3.2 Statistical Analysis Issues

All analyses will be descriptive unless otherwise noted.

Background rates of select pregnancy outcomes and complications are available through MTN-042B but are not appropriate for direct comparison as the study populations differed significantly. MTN-042B included all women who presented to the local delivery facility over an eight week period. By design, women who experienced an early loss would not be captured in this cohort. MTN-042 excluded women with complicated pregnancies and as a consequence rates of pregnancy complications and poor obstetric outcomes are likely to be lower in MTN-042 than in MTN-042B.

Study visit numbers for pre-pregnancy outcome visits were defined in relation to enrollment (e.g., visit 10/Week 8 visit occurred 8 weeks after enrollment). Summaries by visit are by study visit unless otherwise noted. Some study procedures were completed at visits corresponding to certain weeks of gestation, and since mothers were enrolled at different gestational ages this means that these procedures were not completed at the same study visit for all participants. Some analyses will be performed by grouping these gestational-week-dependent visits together, instead of summarizing by study visit. Gestational age at enrollment is recorded on the Pregnancy Assessment CRF.

Relevant gestational-week-dependent visits correspond to the following study visits:

4-week visit corresponding to, or immediately before, 36th week of gestation:

- Visit 10 if gestational age 25-28 weeks
- Visit 14 if gestational age 21-24 weeks
- Visit 18 if gestational age 17-20 weeks
- Visit 22 if gestational age 13-16 weeks
- Visit 26 if gestational age 12 weeks

4-week visit corresponding to, or immediately following, the 30th week of gestation:

- Visit 6 if gestational age 26-29 weeks
- Visit 10 if gestational age 22-25 weeks
- Visit 14 if gestational age 18-21 weeks
- Visit 18 if gestational age 14-17 weeks
- Visit 22 if gestational age 12-13 weeks

Visit corresponding to, or immediately following, the 28th week of gestation:

- Visit 10 if gestational age 20-23 weeks
- Visit 14 if gestational age 16-19 weeks
- Visit 18 if gestational age 12-15 weeks

Participants were instructed to use study product until they went into labor. This complicates analyses of laboratory adherence measures (see Section 9.3) taken at the Visit 101 – PPO Visit, since this visit could occur up to 14 days after the pregnancy outcome, i.e., this visit will include time when the participant was expected to not be using study product and drug levels are expected to drop quickly following product discontinuation. This applies to all three laboratory adherence measures, including residual drug levels in VRs since the residual drug measure adjusts for how long the participant had the ring.

Some laboratory adherence measures were tested for a subset of the study population. TFV-DP and FTC-TP were tested for a subset of Cohort 1 mothers (30% of the mothers with a collected sample) (all collected samples were tested for infants, and for mothers in Cohorts 2 and 3). Plasma DPV was tested for a subset of mothers in all three cohorts (50% of the mothers with a collected sample) (all collected samples were tested for infants).

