9.2 Infant Drug Levels

The number and percentage of infants with detectable drug levels in each study arm for each sample type will be summarized using descriptive statistics in tables overall for each of the three cohorts, and overall for the three cohorts combined. Participants with a drug level for the assay corresponding to their mother's randomization arm (i.e., plasma DPV concentration for the DPV VR arm, blood TFV-DP and FTC-TP concentration for the FTC/TDF arm) above the lower limit of quantification (LLOQ) at the PPO visit (including interim PPO visits) will be considered to have a detectable drug level for that sample type; otherwise, the participant will be considered to have an undetectable drug level for that sample type. If a participant has multiple concentrations at a visit, they will be considered to have a detectable drug level for that sample type if any of the concentrations are above the LLOQ. The denominator will be the number of infants in the analysis set with at least one valid drug result for the assay corresponding to their mother's randomization arm. Valid drug results are defined as any result that does not have any of the following censor codes: A, D, O, P, X, Z.

Additionally, drug concentration levels at the PPO visit (including interim PPO visits) will be summarized using geometric mean, geometric coefficient of variation (CV), arithmetic mean, standard deviation (SD), median, interquartile range (IQR), and range (minimum, maximum). The CV will be calculated as $100 \times$ standard deviation / Mean of the concentration values. Drug concentrations below the LLOQ will be treated as having a value of half the LLOQ for these summaries. Drug concentrations from assays that do not correspond to the mother's randomization arm, or which have any of the censor code A, D, O, P, X, and/or Z, will be excluded from these summaries.

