- If sample was collected within 6 weeks (i.e., specimen collection date - randomization date + 1 day \leq 42 days):
Red (<150 fmol/punch)
Yellow (150 fmol/punch – 599 fmol/punch)
Green (\geq 600 fmol/punch)
- If sample was collected more than 6 weeks (i.e., specimen collection date – randomization date + 1 day $>$ 42 days) after randomization date:
Red (<200 fmol/punch)
Yellow (200 fmol/punch – 649 fmol/punch)
Green (\geq 650 fmol/punch)

Plasma DPV:

Red (<LLOQ (i.e., < 20 pg/mL))

Yellow (LLOQ – 95 pg/mL, inclusive)

Green ($>$ 95 pg/mL)

These categories will be summarized in terms of the number and percentage of participant visits, by visit (including all visits combined) and study arm for each of the three cohorts, and by visit and study arm for the three cohorts combined. The denominator will be the number of valid samples at the visit.

Adherence will also be summarized at a participant level for all three measures, with participants categorized as either “ever exposed” (if they have at least one measure in the Yellow or Green category) or “never exposed” (if they have no measures in the Yellow or Green categories). These categories will be summarized by number and percentage of participants by study arm for each of the three cohorts, and by study arm for the three cohorts combined. The denominator will be the number of participants with at least one valid sample.

Additional exploratory analyses of Blood TFV-DP categories may be done if additional information regarding adherence cutoffs becomes available. These exploratory analyses would not be part of the CSR.

Participant report of frequency of study product use will be summarized by visit for each of the three cohorts, and for the three cohorts combined. For participants randomized to the FTC/TDF arm this will be the responses to the “In the past 4 weeks, how often did you miss taking the pills” item on the Tablet Adherence CRF (possible responses are “never”, “rarely”, or “often”). For participants randomized to the DPV VR arm this will be the responses to the “in the past 4 weeks, how often was the ring out of your vagina for any extended period of time, that is more than 12 hours in a row?”, “in the past 4 weeks, how often was the ring out of your vagina, even for just a minute excluding expected instances when a ring was briefly removed and replaced with a new ring?”, and “was the ring ever removed (in the past 4 weeks)?” items on the Ring Adherence CRF.

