The number of days (*days* in the above equation) is calculated by taking the specimen collection date – “date returned ring #1 was provided” + 1 day (or “date returned ring #2 was provided”), unless the specimen collection date is after the participant’s pregnancy outcome date, in which the duration is calculated as the pregnancy outcome date – “date returned ring #1 was provided” + 1 day.

Ring lot number is determined by linking the “date returned ring #1/#2 was provided” to the Pharmacy Dispensation CRF “date study product dispensed” and taking the “vaginal ring #1 lot number” or “vaginal ring #2 lot number”, as appropriate. That lot number is linked to the manufacturer record of the concentration for that lot ($conc_m$ above).

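### Maternal blood drawn after the pregnancy outcome is graded with on-use adherence cut-offs and pooled with on-use samples, although the SAP itself says levels will have fallen

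*SAP*

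**What the plan says.** Section 3.2 sets out the timing problem. "Participants were instructed to use study product until they went into labor", while for Visit 101 "this visit could occur up to 14 days after the pregnancy outcome". It adds that "this visit will include time when the participant was expected to not be using study product and drug levels are expected to drop quickly", and says that all three laboratory measures are affected, "including residual drug levels in VRs since the residual drug measure adjusts for how long the participant had the ring".

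Section 9.3 then defines Red, Yellow and Green. For plasma DPV the cut-offs are 20 and 95 pg/mL. For TFV-DP they are 150 and 600 fmol/punch up to 42 days after randomization, and 200 and 650 afterwards. On reporting it says: "These categories will be summarized in terms of the number and percentage of participant visits, by visit (including all visits combined) and study arm". The denominator is every valid sample. A mother counts as ever exposed with one Yellow or Green result at any visit, and otherwise as never exposed. Blood taken at an unscheduled time is assigned back to the last visit at which collection was expected.

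Appendix III counts ring days up to specimen collection, "unless the specimen collection date is after the participant"'s pregnancy outcome date, in which case counting stops at the outcome.

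For infants, Section 9.2 pools everything drawn at the post-pregnancy-outcome visit: "Additionally, drug concentration levels at the PPO visit (including interim PPO visits) will be summarized using geometric mean, geometric coefficient of variation (CV"). It then gives the CV as 100 times the standard deviation over the mean of the concentrations. Table 11 lets this infant visit fall up to 14 days after the outcome.

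**The concern.** The SAP identifies a timing artefact in its own adherence data and then specifies an analysis that does not deal with it for the two blood measures. A low Visit 101 blood level can reflect days since the product was stopped as planned rather than poor use before labor. Adding such results to the combined row makes adherence look worse than it was, by an amount that depends on how soon after delivery women were seen.

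The participant-level table is exposed in a narrower way. A woman who delivers before any on-use sample is drawn, or whose on-use samples are invalid, is judged on a post-outcome sample alone and may be counted as never exposed.

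Adherence and infant drug levels are secondary endpoints and are what readers will use to interpret the safety results.

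**Working it through.** The SAP gives no figure of its own to reproduce, and no half-life, draw-time distribution or blood-sampling schedule. The check compares the rules and then asks under what conditions they misgrade a sample.

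**1. Treatment of time off product, by measure**
- Ring (Appendix III): day count stops at the outcome date.
- Plasma DPV (9.3): fixed cut-offs, no rule on time since last use.
- TFV-DP (9.3): cut-offs depend on time since randomization, so the start of use is allowed for but the end is not.
- The 7-day limit after discontinuation in the Product Exposure Set (3.1) is not invoked in 9.3.

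**2. When does a Green level become Red?** Assume first-order decay. The number of half-lives needed is n = log2(C0/C1), and the longest half-life that gives the fall in t days is t/n.
- DPV, 95 to 20 pg/mL: n = log2(4.75) = 2.25. Red by day 14 if the half-life is at most 14/2.25 = 6.2 days; by day 7 if at most 3.1 days.
- DPV from an assumed 300 pg/mL to 20: n = log2(15) = 3.91. Limits 3.6 days (day 14) and 1.8 days (day 7). With an assumed half-life of 4 days, Red is reached at 4 × 3.91 = 15.6 days, just outside the window.
- TFV-DP, 650 to 200: n = 1.70, limit 14/1.70 = 8.2 days. TFV-DP, 600 to 150: n = 2.00, limit 7.0 days.
- TFV-DP with an assumed half-life of 14 to 21 days: 650 falls to 650 × 0.5^(14/14) = 325 or 650 × 0.5^(14/21) = 409 by day 14. That is Yellow, not Red.

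**3. Effect on the pooled row.** For a mother with k Green on-use samples and one Visit 101 sample decayed to Red, the pooled Red share is 1/(k+1): 50% for k = 1, 33% for k = 2, 25% for k = 3, 16.7% for k = 5. It is 0% in every case once the post-outcome sample is on its own line.

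**4. Effect on the participant-level label.** With k of 1 or more, ever exposed is unaffected. With k = 0 and a decayed Visit 101 sample, the label is never exposed. In Cohort 1, TFV-DP was tested for 30% of mothers with a sample. With a planned tablet arm of 50 that is about 0.30 × 50 = 15 women, so one mislabelled woman is about 1/15 = 7 percentage points.

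**5. Ring.** Assume a true rate of 4.2 mg per 28 days, 14 days of use and return 14 days after the outcome. Drug released is 4.2 × 14/28 = 2.1 mg. With the cap: 2.1/15 × 28 = 3.92. Without it: 2.1/29 × 28 = 2.03. The cap removes nearly all of the distortion; the remaining shortfall comes from the added day. Neither value is Red (0.9 or below).

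**6. CV in Section 9.2.** The stated formula is the arithmetic CV. The geometric CV is 100 × sqrt(exp(s²) − 1), with s the SD of the natural-log concentrations. As an illustration only, take two values, 10 pg/mL (half of the 20 pg/mL LLOQ) and 95 pg/mL. Arithmetic: mean 52.5, SD 85/√2 = 60.1, CV 114%. Geometric: s = ln(9.5)/√2 = 1.592, s² = 2.534, CV = 100 × sqrt(12.61 − 1) = 341%. The choice of formula matters.

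**The case against.** The best defence is that the SAP discloses the limitation and reports by visit. Visit 101 has its own row, and on-use rows are unaffected apart from any unscheduled post-delivery draw assigned back to them. The colours count participant visits, not women, and one earlier Yellow or Green sample secures the ever-exposed label. The analysis is descriptive and no test or decision depends on it. All of this stands, and it confines the defect to the pooled row and to mothers without an informative on-use sample. It does not explain why a combined row should include samples that the SAP says were taken off product.

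A reader might infer more than the document supports:
- *That adherent mothers in general will be called Red.* This needs a short half-life and a late draw; with a long TFV-DP half-life only Green to Yellow follows.
- *That all three measures are uncorrected.* Section 3.2 suggests so, but Appendix III caps the ring clock.
- *That infant exposure is understated.* The sentence on quickly falling levels concerns the maternal adherence measures. The SAP gives no infant decay rate or draw times, and the infant visit is targeted as early as possible after the outcome.
- *That Visit 101 is a third or more of Cohort 1 samples.* In-person visits are not sample counts, and the blood schedule is not in the SAP.
- *That samples after any product discontinuation should go.* Removing women who stopped early would hide genuine non-use and inflate adherence.

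**Conclusion.** The point holds for maternal plasma DPV and TFV-DP. Followed as written, Section 9.3 mixes on-use and post-use samples in its combined adherence row and can label a mother never exposed on a post-outcome sample alone. The distortion makes adherence look lower. Its size cannot be fixed from the SAP: it rests on assumed first-order decay, unknown half-lives and unknown draw times, and ranges from nothing for same-day draws to a 50% pooled Red share for a mother with one on-use sample. The statement in Section 3.2 that all three measures are affected does not sit well with the ring cap in Appendix III.

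For infants the supported statement is weaker: late draws may understate levels, by an unknown amount. The geometric CV error is definite. The change should be made, but no primary result depends on it.

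**What to change.** - **Section 9.3, pooled row:** leave plasma DPV and TFV-DP samples collected after the pregnancy outcome date out of the all-visits row. Decide this by collection date, so that unscheduled samples assigned back to an earlier visit are also caught. Show these samples on a separate line with days from outcome to draw.
- **Section 9.3, participant level:** do not label a mother never exposed on post-outcome samples alone. A Yellow or Green post-outcome sample still counts as ever exposed.
- **Section 9.3, early stoppers:** do not exclude samples because product was discontinued before the outcome.
- **Section 3.2 and Appendix III:** reconcile the statement about all three measures with the ring cap.
- **Section 9.2:** report infant age at draw alongside the planned summaries, and compute the geometric CV as 100 × sqrt(exp(s²) − 1), with s the SD of the natural-log concentrations.

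The cost is SAP wording and a few table rows, since the outcome and collection dates are already used elsewhere in the plan. The pooled maternal row will have fewer samples, because most Visit 101 blood samples move to their own line. A mother with only uninformative post-outcome samples needs a separate, not-assessable category.

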4. INTERIM ANALYSIS AND DATA MONITORING COMMITTEE

No DSMB oversight was planned for this study. The MTN SMC conducted interim reviews of study progress, including rates of participant accrual, retention, completion of primary and secondary endpoint assessments, and study or laboratory issues. These reviews took place after all pregnancy outcomes had occurred for Cohort 1, after all pregnancy outcomes had occurred for Cohort 2, and after all mothers had been enrolled for Cohort 3.

An interim review of the safety data by the Interim Review Panel (IRP) was planned and conducted after each cohort completed scheduled participation and prior to beginning accrual in the next scheduled cohort. Planned IRP analyses are documented in the IRP SAP for MTN-042 Cohort 1 and the IRP SAP for MTN-042 Cohort 2.

5. GENERAL ANALYSIS METHODS

When the use of descriptive statistics to assess group characteristics or differences is described, the following methods will be used: for categorical variables, the number and percent in each category; for continuous variables, the mean, median, standard deviation, quartiles, and range (minimum, maximum).

Descriptions of tabular summaries that are “by study arm and overall” indicate that the table should have columns summarizing each arm as well as a column summarizing the combined arms.

Tabular summaries by visit do not include interim visits, unless otherwise noted. Results from all visits (including interim visits) will be included in listings.

[figure not shown]
In addition to separate analyses/summaries for each of the three cohorts, an exploratory analysis will split Cohort 3 participants into two groups based on gestational age (20 0/7 weeks through 29 6/7 weeks and 12 0/7 weeks through 19 6/7 weeks) as collected on the Pregnancy Assessment CRF. These ages were originally going to be two separate cohorts in Protocol Version 1.0 before being combined into one cohort in Protocol Version 2.0. These exploratory analyses splitting Cohort 3 will be done only for certain analyses, as specified in this document.

6. TRIAL PARTICIPANT DISPOSITION

6.1 Disposition of Participants

The number of pregnant women screened, screened out (with reasons for not enrolling), randomized to each study arm (with reasons for not receiving assigned intervention), with obtainable pregnancy outcomes (with reasons outcome was not obtainable), completing study follow-up (with reasons study follow-up was not completed), the number of infants enrolled (with reasons not enrolled), and number of infants completing study follow-up (with reasons infant follow-up was not completed) will be presented in a CONSORT flow diagram. Separate diagrams will be used for each cohort.

Figure 1. Mock CONSORT Diagram

6.2 Treatment Exposure

As described in Section 3.1 Analysis Set(s), the Product Exposure analysis set will exclude endpoint data that occurs > 7 days after study product discontinuation, and will exclude participants who never received study product.

Study duration, infant study duration, on product duration, on study pregnancy duration, and estimated gestational age at pregnancy outcome will be summarized as continuous variable in tables, by study arm and overall for each of the three cohorts, and for the three cohorts combined.

Study duration will be calculated as the date of study exit (Study Termination CRF) minus the participant's randomization date + 1 day, unless the participant had a termination reason of "Lost to follow-up". If a participant was lost to follow-up then their study duration will be calculated as the date of their last attended visit minus their randomization date + 1 day. The last attended visit is either the last visit with a completed Follow-up Visit Summary CRF, or the last Interim Visit Summary CRF where at least one study procedure was completed (per Interim Visit Summary CRF, "What study procedures were completed at this visit? Select all that apply" item), whichever occurred last.

Infant study duration will be calculated as the date of study exit (Study Termination CRF) minus the infant's birth date + 1 day, unless the infant had a termination reason of "Lost to follow-up". If an infant was lost to follow-up then their study duration will be calculated as the date of their last attended visit minus their birth date + 1 day. The last attended visit is either the last visit with a completed Infant Follow-up Visit Summary CRF, or the last Infant Interim Visit Summary CRF where at least one study procedure was completed (per Interim Visit Summary CRF, "What study procedures were completed at this visit? Select all that apply" item), whichever occurred last.

On product duration will be calculated as the date of product discontinuation (Discontinuation of Study Product CRF) minus the participant's randomization date + 1 day. Only participants who ever received study product will be included in this summary.

On study pregnancy duration will be calculated as the date of the pregnancy outcome (outcome date on Pregnancy Outcome CRF) minus the participant's randomization date + 1 day. Only participants with an obtainable pregnancy outcome will be included in this summary.

Estimated gestational age at pregnancy outcome will be calculated as the date of the pregnancy outcome minus the date of the participant's pregnancy assessment (Pregnancy Assessment CRF) + 1 day, plus the participant's estimated gestational age (in days) at their pregnancy assessment (Pregnancy Assessment CRF), and will be reported in weeks (e.g., an estimated gestational age of 38 weeks 6/7 days would be treated as 38.86 weeks for this summary). Note that this derivation will be used even if the participant had an available gestational age by best estimation at delivery on the Pregnancy Outcome CRF.

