8.3 Pregnancy Outcomes

The number and percentage of pregnancy outcomes (full term live birth [≥ 37 0/7 weeks], premature live birth [< 37 0/7 weeks], stillbirth/intrauterine fetal demise [≥ 20 0/7 weeks], and spontaneous abortion [< 20 0/7 weeks]) and the exact binomial confidence intervals for those proportions will be summarized by study arm and overall for each of the three cohorts, and by study arm and overall for the three cohorts combined. This analysis will include all participants in the analysis set who had an obtainable pregnancy outcome. If a participant was found to have a non-singleton pregnancy after enrollment then each outcome from that pregnancy will be included in this analysis.

A secondary analysis will be conducted by repeating the pregnancy outcome summaries for only participants who received study product (i.e., the participants in the Product Exposure Set).

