17	V10 (GA 25) V14 (GA 29)	V14 (GA 33)	V18 (GA 33)	V21 (GA 36)	V22 (GA 37)	V23 (GA 38)	V24 (GA 39)	V25 (GA 40)	V26 (GA 41)					
16	V10 (GA 24) V14 (GA 28)	V14 (GA 32)		V22 (GA 36)	V23 (GA 37)	V24 (GA 38)	V25 (GA 39)	V26 (GA 40)	V27 (GA 41)					
15	V10 (GA 23) V14 (GA 27)	V14 (GA 31)		V22 (GA 35)	V23 (GA 36)	V24 (GA 37)	V25 (GA 38)	V26 (GA 39)	V27 (GA 40)	V28 (GA 41)				
14	V10 (GA 22) V14 (GA 26)	V14 (GA 30)		V22 (GA 34)		V24 (GA 36)	V25 (GA 37)	V26 (GA 38)	V27 (GA 39)	V28 (GA 40)	V29 (GA 41)			
13	V10 (GA 21) V14 (GA 25)	V14 (GA 29)		V22 (GA 33)			V25 (GA 36)	V26 (GA 37)	V27 (GA 38)	V28 (GA 39)	V29 (GA 40)	V30 (GA 41)		
12	V10 (GA 20) V14 (GA 24)	V14 (GA 28)		V22 (GA 32)				V26 (GA 36)	V27 (GA 37)	V28 (GA 38)	V29 (GA 39)	V30 (GA 40)	V31 (GA 41)	

Cells shaded blue represent expected phone contact visits. Cells shaded yellow represent expected in-person visits. The parenthetical "GA x" displays the gestational age in weeks of the participant at that visit. Visits in this table are only considered expected up until the participant's pregnancy outcome.

Note that these gestational ages at enrollment groups did not have any expected visits after Visit 6 and prior to Visit 10, after Visit 10 and prior to Visit 14, after Visit 14 and prior to Visit 18, and after V18 and prior to Visit 21, and these visits are omitted from Table 7.

13. APPENDIX II Visit Timing Requirements

Table 8: Visit Timing Requirements for Mothers in Cohort 1

Visit	Target Day	Window Opens	Window Closes
Visit 1 - Screening	N/A	N/A	
Visit 2 - Day 0 Enrollment	0	Up to 35 days after screening informed consent date	
Visit 3 - Week 1 Phone Contact	7	6 days prior to target	2 days after target
Visit 4 - Week 2 Bi-weekly Visit	14	4 days prior to target	4 days after target
Visit 5 - Week 3 Phone Contact	21	2 days prior to target	2 days after target
Visit 6 - Week 4 Bi-weekly Visit	28	4 days prior to target	4 days after target
Visit 7 - Week 5 Phone Contact (women who enroll at 36 weeks GA only)	35	2 days prior to target	2 days after target
PPO Visit	as soon after the PO as possible	Pregnancy Outcome	14 days after target
1-Week PPO Phone Contact*	7 days after PO	6 days prior to target	7 days after target
6-Week PPO Visit/SEV	42 days after PO	13 days prior to target	13 days after target

*The 1-Week PPO Phone Contact may be skipped if the PPO Visit occurs within the visit window for this phone contact

Table 9: Visit Timing Requirements for Mothers in Cohort 2

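### The Section 6.2 derivation of gestational age at pregnancy outcome adds one day too many, so every value in that summary is 1 day (0.14 week) too high

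*SAP*

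**What the plan says.** SAP Section 6.2 lists gestational age at outcome among the quantities to be tabulated by arm and overall, per cohort and for the cohorts combined: "estimated gestational age at pregnancy outcome will be summarized as continuous variable in tables". The derivation has two parts. The first is the elapsed time, the outcome date minus the date of the "pregnancy assessment (Pregnancy Assessment CRF) + 1 day, plus the" second part, which is the "estimated gestational age (in days) at their pregnancy assessment (Pregnancy Assessment CRF").

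The result is converted to decimal weeks: "an estimated gestational age of 38 weeks 6/7 days would be treated as 38.86 weeks for this summary". The section then gives this rule priority over a second source that may be on file: "Note that this derivation will be used even if the participant had an available gestational age by best estimation at delivery".

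The four durations defined just before it (study, infant study, on product, and on-study pregnancy) all carry the same added day.

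Section 8.3 defines the live-birth categories as "full term live birth [≥ 37 0/7 weeks], premature live birth [< 37 0/7 weeks"] and separates the two kinds of pregnancy loss at 20 0/7 weeks. It does not name the gestational age source that assigns a category, and it does not refer to Section 6.2.

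**The concern.** An added day is a legitimate choice when the quantity is a number of days on study and both end days are to count. Gestational age at outcome is a different kind of quantity: a value known on one date is carried forward to another. The recorded value already includes the assessment date, so only the difference between the two dates should be added.

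What is at stake is the accuracy of a descriptive table in a trial whose subject is pregnancy. The error is the same for every woman, and at the two decimals used in the SAP's own example it is visible. Because the rule applies even where a best estimate at delivery exists, that estimate cannot correct the value in this summary.

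**Working it through.** **Inputs**

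- Rule as written (Section 6.2): GA at outcome = (outcome date − assessment date + 1) + GA at assessment, in days.
- Rule for carrying a gestational age forward: GA at outcome = (outcome date − assessment date) + GA at assessment.
- Cut-offs (Section 8.3): 37 0/7 weeks = 37 × 7 = 259 days; 20 0/7 weeks = 20 × 7 = 140 days.
- Expected gestational ages at visits: Appendix I, Tables 3, 4 and 7. Target days, with enrollment as day 0: Appendix II, Tables 8 to 10. For example, "Visit 7 - Week 5 Phone Contact (women who enroll at 36 weeks GA only") has target day 35.

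**The SAP's own figure.** (38 × 7 + 6)/7 = 272/7 = 38.86 weeks. The conversion to weeks is reproduced. The fault lies in the step before it.

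**Limiting case.** Take a woman assessed and delivered on the same date at 36 6/7, which is 36 × 7 + 6 = 258 days. The rule gives (0 + 1) + 258 = 259 days, or 37 0/7. Her gestational age on that date was recorded as 36 6/7, so the rule assigns two values to one date.

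**Further cases**, taking the gestational age as assessed at enrollment where Appendix I is the comparison:

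| Case | GA at assessment (days) | Days elapsed | Rule as written | Without the extra day | Appendix I |
|---|---|---|---|---|---|
| Enrolled 36 6/7, Week 5 | 258 | 35 | 294 = 42 0/7 | 293 = 41 6/7 | GA 41 |
| Enrolled 30 6/7, Week 6 | 216 | 42 | 259 = 37 0/7 | 258 = 36 6/7 | GA 36 |
| Enrolled 12 6/7, Week 29 | 90 | 203 | 294 = 42 0/7 | 293 = 41 6/7 | GA 41 |
| Assessed 12 0/7, loss 55 days later | 84 | 55 | 140 = 20 0/7 | 139 = 19 6/7 | not applicable |

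Appendix I shows gestational age in whole weeks, so it exposes the extra day only for women enrolled on the last day of a gestational week. For a woman enrolled at 36 0/7, day 35 is 41 0/7 without the extra day and 41 1/7 with it, and both read as GA 41. For women enrolled at 6/7, only the version without the extra day agrees with the tables.

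**Does the day-count convention matter?** No. Whether dating starts at day 0 or day 1, the convention is already inside the recorded gestational age, and two gestational ages in the same woman differ by exactly the difference of their dates. The rule as written returns the true value plus 1 day under both conventions.

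**Could the added day belong to the assessment date instead?** Then the elapsed time is outcome date − (assessment date + 1), and a birth at 36 6/7 computes as 36 5/7, one day too low. Neither reading is right.

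**Effect on the table.** A constant of 1 day, 1/7 = 0.14 week, is added to every observation. Under the continuous summaries set out in Section 5, the mean, median, quartiles, minimum and maximum each rise by 0.14 week. The standard deviation, the width of the range and any difference between arms are unchanged.

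**The case against.** The strongest answer is that the effect is small and confined to one table. Gestational age at outcome is assigned only to a continuous summary under treatment exposure. A shift of 0.14 week, equal in both arms, does not alter the comparison of arms. The Poisson offsets in Sections 8.1 and 8.2 are on-product days and infant study days, so they do not involve it. All of that stands. It limits the size of the point but does not make the derivation right.

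A reader might infer more: that births at 36 6/7 will be counted as full term, and losses at 19 6/7 as losses at or after 20 weeks, so that the primary pregnancy outcome is misclassified and premature birth understated. The SAP does not support that inference:

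- Section 8.3 neither cites Section 6.2 nor names this variable. Where the SAP reuses a 6.2 derivation, in Sections 8.1 and 8.2, it says so explicitly.
- The note giving the derivation priority over the best estimate at delivery concerns the 6.2 variable. It does not say that the best estimate is set aside for the 8.3 categories.
- Section 2.6 expects about 5% premature live births, but the SAP gives no share of births falling on the single day 36 6/7. Any figure for a shifted premature-birth rate would need that outside assumption as well as the unstated use in 8.3, so none is offered here.

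What remains for Section 8.3 is conditional. If a programmer took this variable, the only derivation of gestational age at outcome in the SAP, to assign the categories, outcomes at 36 6/7 and 19 6/7 would cross the cut-offs. If the categories come from another source, the derived value can still disagree with the reported category for those women.

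**Conclusion.** The derivation is wrong as written. It overstates gestational age at outcome by exactly 1 day (0.14 week) for every woman with a derived value, in both arms and all cohorts. The outcome date itself is unaffected. The result needs no assumption beyond the recorded gestational age being the value on the assessment date. The comparison with Appendix I also takes that assessment as made at enrollment.

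The certain consequence is that every location statistic in the 6.2 summary is too high, while spread and between-arm differences are correct. No primary or secondary endpoint is stated to depend on the variable. This is therefore a small but definite correction to a descriptive table, and it does not show that the primary pregnancy outcome is misclassified.

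**What to change.** Remove the added day from this derivation only:

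GA at outcome (days) = GA at assessment (days) + (outcome date − assessment date), then divide by 7 for the report in weeks.

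Leave the added day in the four durations, where an inclusive count is a valid choice. Do not use the uncorrected value to assign or cross-check the Section 8.3 categories; a short sentence naming the gestational age source for those categories would settle it.

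The cost is one SAP line and one program line, plus the optional sentence in Section 8.3. No data collection changes. If the table has already been produced, it needs rerunning; its location statistics fall by 0.14 week and its standard deviations stay as they are.
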